### 5.3. Clinical trial for angina pectoris

An open label clinical trial was conducted to assess ACP administration for severe angina pectoris at Siriraj Hospital in Bangkok, Thailand, the largest and most renowned academic hospital in Thailand (Tresukosol et al., 2006). The study was approved by the hospital's ethics committee, which is the regulatory body in charge with supervising clinical trials in Thailand.

Similar to the CLI pilot study, maximal efforts were made to ensure proper conduct and supervision of the clinical trials in compliance with Good Clinical Practices. As required by international standards of clinical trials, Hemostemix (formerly TheraVitae Ltd.) established a dedicated team of professionals to supervise and monitor both clinical trials in Thailand (CLI and angina pectoris). The team was led by a practicing Israeli-licensed physician with extensive clinical experience.

The objectives of the trial were to determine the safety and feasibility of intracoronary injection of blood-derived autologous ACPs in relieving symptoms of angina pectoris in patients on standard of care with no option for revascularization procedures (angioplasty or CABG).

Twenty-four patients with chronic stable angina pectoris on standard of care drug therapy were enrolled and signed the informed consent. ACPs ( $32.3 \times 10^6 \pm 4.2 \times 10^6$ ) were injected via a catheter with proximal

balloon occlusion of the coronary artery supplying the ischemic myocardium. The patients were assessed prior to and 3 and 6 months after the treatment by using the Canadian Cardiovascular Scale (CCS), the six-minute walking test (6MW), their exercise capacity (METs), and perfusion defect measurements.

### 5.3.2. Efficacy data

Symptoms and perfusion defects were significantly improved relative to baseline. CCS decreased from  $2.17 \pm 0.18$  at baseline to  $1.04 \pm 0.04$  at 3 and  $1.13 \pm 0.10$  at 6 months. Six minute walking ability increased from  $346.7 \pm 27.3$  meters to  $409.7 \pm 25.8$  meters and  $427 \pm 25.6$  meters at 3 and 6 months, respectively. METs values, analyzed in 20 patients, increased from  $5.5 \pm 0.49$  to  $6.5 \pm 0.6$  and  $6.8 \pm 0.59$  at 3 and 6 months. Perfusion defects in the territory of the target vessel decreased from  $39.37\% \pm 5.65\%$  to  $24.38\% \pm 5.41\%$  and  $24.91\% \pm 5.57\%$  at 3 and 6 months. The results of this study support the assumption that intracoronary injection of autologous ACPs derived from non-mobilized peripheral blood into patients with chronic stable angina is safe, improves anginal symptoms, and alleviates myocardial ischemia at 3 and 6 months.

#### 5.4. Conclusion

Although very encouraging efficacy was observed in comparison to best available care, the main reason to perform a Phase 2 trial is to continue to evaluate the safety of the therapy in parallel with its effectiveness in a larger cohort of patients. The data presented show that the therapy demonstrated a favourable safety profile in patients suffering from severe heart disease.

An extensive search of the literature was performed to find potential adverse effects of non-mobilised (by G-CSF) autologous blood-derived progenitor cells on patients. The search was performed on the database of the US National Library of Medicine and included articles published in the period 1998-2011. No articles were found that reported potential risks of such an approach. The use of autologous blood-derived progenitor cells (mainly bone-marrow derived) dates back decades; their main therapeutic use was for hematological malignancies. The potential positive effect that some of those cells may demonstrate in cardiovascular disorders was discovered in the last twenty years. However, regardless of the indication, the use of these cells does not raise safety concerns.

It is emphasized that in order to offer the patients the greatest chances of recovery, the best existing medical care will be provided to all subjects regardless of the group to which they are randomized.

was better ( $p=0.01$ ) in the two cell-implanted groups. Scar size of the intramyocardial ACP group was smaller ( $p=0.02$ ) than the one in the control group. The scar size was smaller in the intracoronary ACP group than the control group, however, the difference was not statistically significant ( $p=0.06$ ). The grafted cells were detected four weeks after implantation by immunohistochemistry: antibodies against myosin heavy chain and troponin-I demonstrated muscle-like cells in the scar tissue of the intramyocardial and intracoronary ACP groups suggesting possible cell differentiation and thus a contribution of the implanted cells to tissue repair.

Overall, this study demonstrates the engraftment of ACPs within the infarcted myocardium resulting in significant beneficial effects, including reduced infarct size and improved cardiac function in rats.

## **7. STUDY DESIGN**

This is a prospective, randomized, double-blind, placebo controlled study to assess the efficacy and safety of *ex vivo* autologous ACP administered intramuscularly into the gastrocnemius and dorsal foot muscles of one limb in subjects with CLI.

Subjects treated at each investigative site will provide written informed consent prior to the conduct of any study-related procedures. Thereafter, they will be screened and those meeting the inclusion/exclusion criteria will be enrolled into the trial and undergo all the study procedures including intramuscular injection of autologous ACPs or placebo. The autologous ACPs or placebo will be administered in addition to any conventional treatment that the subject is receiving.

To enable blinding of the assessors and the subjects, the control group will undergo a similar procedure as the treatment group and receive injections into the gastrocnemius and dorsal interossei foot muscles.

Blood samples and cells that are not used in the treatment of subjects with ACPs, e.g., from the placebo group, will be de-identified and may be utilized for manufacturing and quality control testing such as for the development of potency and release assays. Results from the assays and tests may be used to retrospectively examine cell and product characteristics in CLI patients and/or the response to treatment with ACPs.

The placebo will consist of a growth medium, the same medium used in the ACP product suspension. The physician performing the administration of the cells or the placebo may become unblinded to the group to which the subject is randomized while performing the injections of the IMP. Therefore, he/she will not participate in the assessment of the subjects that he/she injected. In the event that the administrator becomes aware of the treatment assigned, every effort will be made to maintain appropriate blinding. All other participants in the study (PI, clinical investigators, other physicians, the subjects, study nurses, coordinators, etc.) will not be aware of the subjects' randomization and will therefore remain blinded to the study.

The study consists of four periods: *Screening, Treatment, safety monitoring* and *Long-term follow-up* periods. Subjects will be followed for one year post treatment.

### 7.1. Screening Period

Screening follows informed consent and begins with the evaluation of the subject at the investigative site to assess eligibility according to the inclusion/exclusion criteria and ends just prior to the administration of the IMP. After signing the informed consent form, the subject will have been formally recruited into the study. The PI or one of the clinical investigators (CI) will decide which leg needs to be treated according to the severity of the disease. In general, the more ischemic limb should be injected.

During this period the following clinical and laboratory examinations will be performed in order to obtain baseline values and verify inclusion/exclusion parameters:

#### 7.1.1. Visit 1: Day –30 to -7

- 1) Evaluation according to the inclusion/exclusion criteria to determine eligibility.
- 2) Obtain and record medical history including current clinical condition, chronic disabilities and current medication/therapy, obtain and record demographical data, review angiography or color flow duplex ultrasound imaging results.
- 3) Assessment of pain on a visual analogue scale (VAS).
- 4) Type and dose of analgesic drug taken by subject.
- 5) Physical examination including Rutherford Assessment.
- 6) Measurement of blood pressure, heart rate, ECG, and temperature (to reduce the likelihood of infection prior to administration of the IMP).
- 7) Leg assessment, including skin color, swelling, limb temperature, presence of ulcers or gangrene, bilaterally.
- 8) Measurement of resting ankle blood pressure using an appropriate adult cuff, bilaterally
- 9) Measurement of toe blood pressure using an appropriate cuff, bilaterally.
- 10) Assessment of leg ulcers, measurement of ulcer size and ulcer photography, bilaterally.
- 11) Vascular quality of life (QoL) questionnaire (Morgan et al., 2008).
- 12) Blood tests:
  - *Hematology:* RBC; Hemoglobin; Hematocrit; WBC; Neutrophils; Lymphocytes; Monocytes; Platelet count, PT (or INR), and aPTT

- *Blood Chemistry:* Blood glucose; Blood urea nitrogen (BUN); Serum creatinine; C-reactive protein; Serum chloride; Serum potassium; Serum sodium; Serum magnesium; Serum albumin; Total serum protein; SGOT/AST; SGPT/ALT; Alkaline phosphatase; Total bilirubin, Creatine phosphokinase (CPK), HbA1c.
- Pregnancy test (serum Beta-hCG), if female of childbearing age.
- Screening for severe contagious infections: HIV-1, HIV-2, HTLV-1, HTLV-2, HBV, HCV.

#### 7.1.2. Visit 2: Day -7 ± 1 day

The following activities should be performed under the supervision of the PI:

- 1) Blood tests:
  - *Hematology:* RBC; Hemoglobin; Hematocrit; WBC; Neutrophils; Lymphocytes; Monocytes; Platelet count, PT (or INR), and aPTT.
  - *Blood Chemistry:* Blood glucose, Blood urea nitrogen (BUN); Serum creatinine; C-reactive protein; Serum chloride; Serum potassium; Serum sodium; Serum magnesium; Serum albumin; Total serum protein; SGOT/AST; SGPT/ALT; Alkaline phosphatase; Total bilirubin, Creatine phosphokinase (CPK), HbA1c.
- 2) Obtain up to 500 ml of the subject's blood by venipuncture (equivalent to typical blood donation volume). The site should be swabbed with betadine solution followed by 70% alcohol swab. Allow to dry by evaporation. A 16g needle is to be used to obtain the blood that will be collected in a transfusion bag containing anticoagulant. It is strongly recommended to draw the entire volume of blood into only one transfusion bag.
- 3) Obtain and send an additional 10 ml blood for blood bacterial culture tests (tested locally at the investigative site's laboratory).
- 4) Complete forms, label blood bag and package for transport to the manufacturing facility.
- 5) Pack the blood and ship to the manufacturing facility.

#### 7.2. Visit 3: Treatment (Day 0)

Preparation of the subject for the treatment procedure will be initiated upon communication by Hemostemix's representative of the estimated date of the investigational product delivery.

If the batch is not released due to failure to meet release specifications, the subject will undergo a repeat Visit 2 within 21 days of the first Visit 2.

If the batch of IMP produced from the second blood also fails to meet specified release criteria, the subject will be withdrawn from the study.

The following clinical assessments will be performed just prior to the administration of the IMP.

- Physical examination, including Rutherford Assessment.
- Standard preoperative monitoring of heart rate, blood pressure, ECG, and body temperature.
- Assessment of ulcers including measurement of area in  $\text{cm}^2$  based on photography of lesions.

#### 7.2.1. IMP administration

The subject will be taken to a treatment room.

The unblinded treating physician, at their discretion, may administer intravenous, intramuscular, and/or oral analgesic medications alone, or in combination with conscious sedation, sufficient to alleviate pain associated with the injection of the investigational product. Additionally, at the discretion of the unblinded treating physician, EMLA (lidocaine and prilocaine) Cream may be applied to the dorsal aspect of the foot to alleviate pain as needed, provided no contraindications for its use exist and the application will not interfere with standard sterilization procedures for the preparation of the injection site. Impaired kidney function may slightly prolong the recovery from conscious sedation.

Under sterile conditions, the subject will then receive a dose of not more than 200 million ACPs in total, containing at least  $5 \times 10^6$  CD31Bright x AcLDL cells and at least  $1 \times 10^6$  CD34 positive cells (which constitute at least 1.5% of the total number of cells injected). The cell suspension will be injected approximately 1.5 cm deep into a minimum of 24 locations in the gastrocnemius muscle of the affected limb and at 6 locations into the dorsal interossei foot muscles (extensor digitorum brevis and extensor hallucis brevis muscles). The 6 injections into the foot should be approximately in one line at the midline of the metatarsus.

The general goal should be to deliver ACPs to the entire ischemic tissue. Since the bulk of the ischemic tissue is in the leg, it is this part of the limb that should receive the bulk of cells. It is therefore required that at least 24 injections of approximately 1ml are administered into the leg.

[figure not shown]
The following recommendations should also be followed:

- The unblinded investigator should try to avoid injections in the proximity of gangrene.
- The unblinded investigator must under no circumstances inject into areas that show signs of cellulitis.
- The unblinded investigator should try to cover the entire ischemic tissue and not inject specifically around chronic wounds.
- The unblinded investigator should start with the injections into the foot. The injections should be performed slowly in order to avoid spill out of liquid containing cells. If the investigator notices that some of the volume injected spills out, he/she should assume that there is not

sufficient space to inject the entire 1 ml into each location in the foot. Therefore, a smaller volume should be injected into the remaining spots in the foot and save the additional volume for the leg injections. This additional volume of cells/placebo should be injected into additional spots in the leg. Thus, in such cases, there may be 1-2 additional injections into the leg. A treatment diagram (example shown below) will be used to document the injections administered to each subject.

- The measurements in the diagram below are only suggestions and the investigator should keep in mind that the principle is to cover as much of the ischemic area as possible. Therefore, he/she may need to reduce or increase the distance between the injection sites depending on the length of the limb.

The administration of the IMP is expected to take no longer than 20-30 minutes, after which the subject will continue to be tightly monitored for a period of 2 hours. The total volume will be 30 ml and approximately 0.75 -1 ml of cell suspension will be implanted into each of 30 injection sites, using a grid. A 23-gauge needle will be used.

The unblinded investigator should ensure that there are no clinical concerns that may prevent the subject from being able to receive the injection on the intended injection date. If the subject is not fit on the planned injection day, he/she should not be injected with the IMP (ACPs/placebo). This subject should be discontinued and if his/her health condition improves he/she can be re-screened into the study. Reasons for being unfit on the injection day include, but are not limited to: acute ischemia, cellulitis or other severe infection in the intended injection leg, wet gangrene, significant deterioration of clinical status, suspected severe concurrent disease with fever  $> 38.4^{\circ}\text{C}$ , etc.

The rationale for the dose of cells and volume is based on several literature reports. Specifically, based on studies of human EPC transplantation into nude mice, Iwaguro et al., calculated that satisfactory reperfusion of the hind limb would require 0.5 to  $2 \times 10^4$  endothelial progenitor cells/gram of animal weight

(approximately 25 grams) (Iwaguro et al., 2002). Since the authors injected the cells systemically, it would be expected that a significantly lower number of cells reached the ischemic tissue. It is difficult to extrapolate the therapeutic equivalence of mouse EPCs and human ACPs. However, the general principle was used in the calculation of the putative dose. Therefore, the minimal dose of the CD31+ and Ac-LDL-uptaking subpopulation of ACPs to be used for subjects will be 5 million cells, which is approximately the average of 10,000 cells per gram of tissue.

A review of the literature was performed and the information was found to support the cell dose proposed in the present study. Elliott et al., 1997, report the volume of the gastrocnemius muscle in 7 patients. Assessments were done by MRI and the approximate volume of the gastrocnemius muscle (Lateral and medial gastrocnemius muscles taken together) was 435-475 cc. Since the density of mammalian skeletal muscle tissue is approximately 1.06 kg/liter, one can assume the approximate weight of the gastrocnemius muscle, with differences depending on the height of the patient, to be approximately 500 grams.

The release specification for ACPs used in the clinical trial for severe angina pectoris and for patients suffering from ischemic heart disease treated on a compassionate basis was 3 million ACPs. In those patients, the treatment with cells showed a good safety profile and encouraging efficacy. The weight of the human heart is roughly 300 grams. By applying the same rationale, since in this proposed study tcells will be injected intramuscularly into the gastrocnemius (which roughly weighs 500 grams), the release specification was set to a minimum of 5 million cells expressing the CD31 marker and uptake of Ac-LDL.

The rationale behind the administration of the treatment is to ensure that the cells can induce their therapeutic effect by being applied across the entire ischemic tissue. It is assumed that intra-muscular injections offer optimal delivery of the cells to reach the ischemic tissue and remain within it. The underlying principle of intramuscular injection is the creation of a cell depot with paracrine activity in the ischemic area that can induce neovascularisation and vasculogenesis most efficiently.

These assumptions are in line with other reports from the literature (Rutherford et al., 1997, Fadini et al., 2010). 33 of 37 reported trials using cells for critical limb ischemia utilized intramuscular rather than intra-arterial injections. Most of the studies used between 20 and 60 injections that were delivered into the gastrocnemius muscle along a symmetric grid. Furthermore, meta-analysis of the 37 studies showed that the intramuscular approach is effective in improving critical CLI endpoints, such as ulcer healing, ankle-brachial index and tissue O2 tension, while intra-arterial injections did not impact those parameters (Fadini et al., 2010).

If a subject is randomized into the control group, he/she will receive placebo which consists of X-Vivo™ 15 only, the same medium in which the ACPs are suspended.

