### **20.1. Randomization Procedure**

After a subject meets the eligibility criteria, he/she will be randomized to one of the two treatment groups, based on a randomization procedure employing a 2:1 assignment ratio, i.e., treatment with ACP-01 or placebo, respectively, using permuted blocks stratified by centers. #

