2. ANALYSIS SETS AND SUBGROUPS / TREATMENT GROUPS

2.1. Analysis sets

Intent-to-Treat (ITT) Analysis Set: The intent to treat (ITT) analysis set will consist of all subjects who have been randomized to the study. In accordance with the ITT principle, all subjects randomized will be kept in their originally assigned treatment group.

Modified Intent-to-Treat (mITT) Analysis Set: The mITT analysis set is a subset of the ITT analysis set. This set will consist of data from all subjects who have been randomized to the study and administered the IMP and had at least one treatment visit post IMP administration. This analysis set will serve as the primary analysis set for efficacy inference.

Per-Protocol (PP) Analysis Set: The per protocol (PP) analysis set is a subset of the mITT analysis set and will consist of all subjects with no major protocol violations that would be considered to impact the analysis of efficacy or safety.

Safety (ST) Analysis Set: The safety analysis set (ST) will consist of all subjects who have been randomized and received the Study IMP. This analysis set will be used as the primary set for safety inference.

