3.3. Efficacy analysis

Efficacy analyses will be carried out in the mITT analysis set by treatment arm.

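### The Day-0 fitness check belongs to a physician called unblinded in one section and possibly unblinded only later in another; if the arm is known at the check, entry to the SAP's primary efficacy set can depend on it

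*Protocol*

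**What the plan says.** **Who checks fitness.** Protocol 7.2.1, on the day of injection: "The unblinded investigator should ensure that there are no clinical concerns that may prevent the subject from being able to receive the injection". The reasons are not closed: "Reasons for being unfit on the injection day include, but are not limited to" is followed by a list that mixes concrete findings (cellulitis, wet gangrene, fever) with a broad judgement about clinical deterioration. For a subject who is not injected: "This subject should be discontinued and if his/her health condition improves he/she can be re-screened into the study".

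**What this physician knows.** Protocol 7.2.1 uses the unblinded label throughout, including for decisions taken before the first injection. Protocol 7, repeated in substance in SAP 1.2.2, is weaker and later in time: the physician "may become unblinded to the group to which the subject is randomized while performing the injections of the IMP". For that reason, "he/she will not participate in the assessment of the subjects that he/she injected".

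**When randomisation happens.** Protocol 20.1: "After a subject meets the eligibility criteria, he/she will be randomized to one of the two treatment groups". No day or visit is named. The schedule in Protocol 14 marks an eligibility assessment at Visit 1 only.

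**What injection controls.** SAP 2.1 defines mITT as "all subjects who have been randomized to the study and administered the IMP and had at least one treatment visit post IMP administration" and makes it the primary efficacy set. SAP 3.3 repeats this: "Efficacy analyses will be carried out in the mITT analysis set by treatment arm". Protocol 20.5 and 20.7 name ITT instead. The sensitivity analyses in SAP 3.3.2.3 include the PP set but no ITT analysis.

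**The concern.** The protocol recognises that the injector may learn the arm, and it bars that person from assessing the subjects he or she injected. It has no matching safeguard one step earlier, where the same person checks who gets injected. Under the SAP, a subject who is not injected leaves the primary efficacy set.

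If the checker knows the arm, borderline subjects could be held back more readily in one arm than in the other. The comparison would then no longer rest on randomisation alone. The PP analysis uses a subset of mITT, and the other sensitivity analyses in SAP 3.3.2.3 address censoring or stratification within the analysed set, so none of them brings withheld subjects back.

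**Working it through.** **1. Can the checker know the arm?**

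| Source | Status of the injecting physician | Timing |
|---|---|---|
| Protocol 7.2.1 | Unblinded, without qualification | Before and during injection |
| Protocol 7; SAP 1.2.2 | May become unblinded | During the injections, so after the fitness check |

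Both cannot describe the moment of the check. The first reading opens a route to arm-dependent entry and the second closes it. No section says when, or whether, the allocation is disclosed to this person.

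**2. Does randomisation come first?** This is an inference. It rests on three points: Protocol 20.1 randomises once eligibility is met; the Protocol 14 table places eligibility at Visit 1; and the mITT definition treats being randomised and being given the IMP as separate conditions. One point weakens it: exclusion criterion W (temperature just before the IMP) can only be judged near Day 0.

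**3. The plan's own precision.** SAP 1.3 states 81% power with 51 events, HR 0.43, one-sided 2.5%; allocation is 2:1.

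- SE of log HR = 1/√(51 × 2/3 × 1/3) = 1/√11.33 = 0.297
- Power = Φ(|ln 0.43|/0.297 − 1.96) = Φ(2.841 − 1.960) = Φ(0.881) = 0.811

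The 81% reproduces and is not in question. The SE is used in step 5.

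**4. Size of the possible bias (all inputs assumed).** True HR is 1, allocation 2:1, event times exponential, censoring at 12 months, median 3 or 8 months. A share f of subjects (5, 10, 15%) has k times the hazard of the rest (1.5, 2, 3). A proportion w of that share is withheld in each arm.

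If all are withheld from ACP-01 and none from placebo, the HR at time zero is 1/(1 − f + fk):

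- f = 5%, k = 1.5: 1/1.025 = 0.976
- f = 15%, k = 3: 1/1.30 = 0.769

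High-risk subjects have their events early, so the placebo arm's excess hazard fades. The HR that solves the Cox score equation over 12 months is therefore nearer 1:

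| Withholding of high-risk subjects | Apparent HR over the grid |
|---|---|
| All in ACP-01, none in placebo | about 0.86 to 0.98 |
| 25 points higher in ACP-01 (75% v 50%, or 50% v 25%) | about 0.96 to 1.00 |
| None in ACP-01, all in placebo | about 1.02 to 1.17 |

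The lowest value is 0.855 if the median of 8 months is set for the whole arm, and 0.863 if it is set for the lower-risk subjects.

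**5. Against the SE of 0.297.**

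- ln 0.86 = −0.151, about 0.51 SE
- ln 0.96 = −0.041, about 0.14 SE
- ln 1.17 = 0.157, about 0.53 SE

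**6. False-positive rate under a second assumed set-up.** No true effect; 65 subjects (43:22); 20% with median 1 month and the rest 4 months; 12 months of follow-up; unstratified log-rank; 20,000 simulations; nominal 2.5% in favour of ACP-01.

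| Poor-prognosis subjects withheld | Rate favouring ACP-01 |
|---|---|
| None | 3.1% |
| 25% in both arms | 3.3% |
| 25% in ACP-01 only (about 2 people) | 4.5% |
| 50% in ACP-01 only (about 4) | 5.7% |
| 100% in ACP-01 only (about 9) | 10.9% |

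Withholding that is equal across arms is close to harmless; the harm comes from a difference between arms.

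**The case against.** The strongest reply is that the unblinded label in 7.2.1 may only name a role. Protocol 7 and SAP 1.2.2 place any unblinding during the injections, and Protocol 12.1 gives placebo in the same type and number of syringes and the same volume. If the checker is still blinded, the route closes. This stands as a possible reading, but the documents do not settle it.

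Other replies also carry weight:

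- Protocol 7.2.1 does not call this person's judgement final or sole, and a blinded judgement alongside it is compatible with the text. Nothing requires one, however.
- Under the protocol's ITT set, a withheld subject stays in. But the endpoint clock starts at IMP treatment (Protocol 20.7.1, SAP 3.3.2.1), so such a subject would still need a defined time origin.
- Several listed reasons are concrete and overlap exclusion criteria C, D, W and Z, which limits discretion for those items but not for the open end of the list.
- SAP 3.2.1 already tabulates randomised, treated and analysed subjects by arm, with reasons for early discontinuation. A gross imbalance would show there.

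A reader might infer from the re-screening sentence that a withheld subject gets a second random allocation. The documents do not say so. Protocol 20.5 and SAP 2.1 keep randomised subjects in their assigned group; only an explicit identity rule for re-screening is missing.

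**Conclusion.** The point holds as a conflict with a conditional consequence. The documents disagree on whether the person checking fitness can know the arm, and the SAP makes injection a condition of its primary efficacy set. If the arm is known, and if randomisation precedes Day 0 as appears likely, entry to that set can depend on the arm.

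A reader might go further and conclude that the injector does know the arm at the check, that selective withholding took place, or that any bias favours ACP-01. The documents support none of these. They report no withheld subjects, and the direction is open: the extreme cases give about 0.86 one way and about 1.17 the other. Both extremes assume complete withholding in one arm and none in the other. A 25-point difference moves the HR to no lower than about 0.96, roughly 0.14 SE at 51 events. The 65 subjects in SAP 1.3 had already been treated, so two-thirds of 65 (about 43) is a count of injected subjects, not a randomised denominator for estimating withholdings.

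The likely size is small to moderate, in a trial where a few people matter. Confidence is medium, because the key premise rests on wording that the documents leave unresolved.

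**What to change.** 1. Reconcile Protocol 7 and SAP 1.2.2 with Protocol 7.2.1: state when the injecting physician is, or may become, unblinded, and whether the allocation is known before the fitness check.
2. In Protocol 7.2.1, have a blinded investigator sign the Day-0 fit/unfit decision, using the Visit 3 examination in Protocol 7.2, before the product goes to the injector. The clinical reasons stay unchanged. The injector may still stop for safety, and each such stop is recorded with its reason.
3. State that a randomised but uninjected subject who is re-screened keeps the original number and arm, in line with Protocol 20.5 and SAP 2.1.
4. Extend the SAP 3.2.1 disposition table to show Day-0 withholdings and re-screenings by arm with reasons, including for subjects already handled. New wording cannot change past decisions, so this listing is the part that shows whether the concern matters for them.
5. Reconcile the primary efficacy set between SAP 2.1/3.3 (mITT) and Protocol 20.5/20.7 (ITT), since the consequence depends on it.

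Cost: some wording, one sign-off line on the Visit 3 form, and extra rows in an existing table. The small downside is that a blinded investigator must sign before hand-over. The retained safety stop leaves the route slightly open, but visible.
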